NCT04496830

Cerebrospinal fluid-biomarkers-based diagnostic and prognostic models for multiple sclerosis

Multi-center study:

- Washington University in St. Louis (WUSTL): [name], [name], [name], [name]
- NIAID/NDS: [name], [name]
- University of Colorado: [name]
- University of Ottawa: [name]
- University of Montana: [name]

Supported by:

The National Multiple Sclerosis Society (NMSS-RG-1907-34348)

Version 3 April 28, 2022

Cerebrospinal fluid-biomarkers-based diagnostic and prognostic models for multiple sclerosis

Multi-center study:

- Washington University in St. Louis (WUSTL): [name], [name], [name], [name]
- NIAID/NDS: [name], [name]
- University of Colorado: [name]
- University of Ottawa: [name]
- University of Montana: [name]

Supported by:

The National Multiple Sclerosis Society (NMSS-RG-1907-34348)

Version 3 April 28, 2022

TABLE OF CONTENTS

SYNOPSIS						
1.	ST	STUDY DESIGN				
2.	SI	SELECTION AND ENROLLMENT OF SUBJECTS				
	2.1 2.2 2.3	Eligibility criteria				
5.	ST	TUDY INTERVENTIONS				
	5.1 5.2 5.3 5.4	Interventions, Administration, and Duration Handling of Study Interventions Concomitant Interventions Adherence Assessment				
6.	CLINICAL AND LABORATORY EVALUATIONS					
	6.1 6.2 6.3	Schedule of Evaluations				
7.	N	IANAGEMENT OF ADVERSE EXPERIENCES				
8.	CRITERIA FOR INTERVENTION DISCONTINUATION					
9.	S	TATISTICAL CONSIDERATIONS				
	9.1 9.2 9.3 9.4 9.5	General Design Issues Outcomes Sample Size and Accrual Data Monitoring Data Analyses				
10.		DATA COLLECTION, SITE MONITORING, AND ADVERSE EXPERIENCE REPORTING				
	10.1 10.2 10.3 10.4	Records to be Kept Role of Data Management Quality Assurance Adverse Experience Reporting				

Page

HUMAN SUBJECTS							
Institutional Review Board (IRB) Review and Informed Consent							
Subject Confidentiality							
Study Modification/Discontinuation							
PUBLICATION OF RESEARCH FINDINGS							
REFERENCES							
APPENDICES							
MODEL INFORMED CONSENT							
(typical appendix items are outcome scales, flowcharts, and organizational charts)							

SYNOPSIS

Study title

Cerebrospinal fluid-biomarkers-based diagnostic and prognostic models for multiple sclerosis

Summary and Objectives

Using machine learning, we have developed from SOMAScan:

- 1. A molecular diagnostic test that differentiates MS from other inflammatory and non-inflammatory central nervous system (CNS) diseases (area under receiver-operator characteristic curve-AUROC of 0.98);
- 2. A molecular test that differentiates relapsing-remitting MS from progressive MS variants (AUROC of 0.91); and
- 3. A molecular test that predicts future rates of disability progression, concordance coefficient of 0.425 (p<0.001).

Because these results are derived from a single research center (NIAID/NDS), it is imperative to determine their performance in real clinical practice settings as a necessary step for their potential regulatory approval. Consequently, this application has 2 specific aims:

AIM 1. To independently validate afore-mentioned CSF-biomarker-based tests for their clinical value within the multicenter Spinal fluid Consortium for MS (SPINCOMS). In Aim 1, each of the 3 defined tests will be validated in 100 new SPINCOMS patients. To validate the prognostic test, 100 MS patients with CSF collected at least 3 years from the date of a follow-up study visit will be evaluated at follow-up examination with standardized clinical outcomes. CSF will be analyzed blinded using pre-defined statistical models.

AIM 2. To explore whether collected CSF-biomarkers point towards pathogenic heterogeneity that may predict patient-specific efficacy for different disease-modifying treatments (DMTs) or identify pathogenic mechanisms not targeted by current DMTs. In Aim 2, clustering analysis will assess pathogenic heterogeneity and explore potential predictors of response to therapy.

1. STUDY DESIGN

Cross-sectional cohort studies (Figure 1.).

- For the MS diagnostic test, we will select 50 patients with definite MS (CIS/RIS excluded) and 50 controls, including 25 non-inflammatory neurological diseases (NIND) that mimic MS (such as patients with vascular-ischemic changes, complex migraines, leukodystrophies, etc.) and 25 other inflammatory neurological diseases (OIND) such as NMO, Susac's syndrome, sarcoidosis, CNS vasculitis.
- 2. For validating the RRMS versus progressive MS classifier, we will select CSF from 50 RRMS and 50 progressive MS patients (25 SPMS and 25 PPMS).

- 3. Cryopreserved CSF samples from these patients will be analyzed blindly using SOMAscan assay. Probability of MS diagnosis and progressive MS diagnosis will be calculated based on published models². Results will then be unblinded and analyzed for accuracy of diagnostic conclusion.
- 4. To evaluate the MS severity score, we will select 50 RRMS and 50 progressive MS (25 PPMS and 25 SPMS).

Figure 1.

1. MS diagnostic classifier

50 MS, 50 non-MS

non-MS diagnoses: ~25 NIND & ~25 OIND with high diagnostic certainty (CIS/RIS must be excluded, unless they progressed to definite MS)

2. RRMS vs PMS classifier

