50 RRMS, 50 PMS

PMS: ~25 PPMS & ~25 SPMS Minimum 3 years from untreated LP Can overlap w Cohort 1 &2

The cohorts of MS patients in 1-3 can overlap.

Select n=100-130 eligible MS patients

Required: ≥ 50 RRMS, ≥ 25 PPMS, ≥ 25 SPMS

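### Test 1 is set at 50 MS v 50 controls although at least 100 MS samples are assayed anyway; using all eligible ones cuts the AUROC SE by about 14% (1–28% by model) and the sensitivity CI width by about 30%, at no assay cost

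*Combined protocol and SAP*

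**What the plan says.** Section 1 item 1 sizes test 1 as follows: "we will select 50 patients with definite MS (CIS/RIS excluded) and 50 controls". Cohort 1 in Figure 1 repeats 50 MS and 50 non-MS. The Synopsis, Aim 1, fixes the total: "each of the 3 defined tests will be validated in 100 new SPINCOMS patients". The development result for this test is an "area under receiver-operator characteristic curve-AUROC of 0.98".

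Item 2 takes CSF from 50 RRMS and 50 progressive MS patients for test 2. Item 3 sends the samples of these patients to SOMAscan and adds: "Probability of MS diagnosis and progressive MS diagnosis will be calculated based on published models". Below the cohorts, Figure 1 states: "The cohorts of MS patients in 1-3 can overlap" and "Select n=100-130 eligible MS patients". Table 1 in Section 2.3 targets 60 + 20 + 20 = 100 MS patients (50 RRMS, 50 progressive) and 30 + 10 + 10 = 50 non-MS patients.

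On who counts as MS, item 1 excludes CIS and RIS without qualification, while Figure 1 says "CIS/RIS must be excluded, unless they progressed to definite MS". Section 2.1 requires a 2017 McDonald diagnosis at the follow-up visit. The data-collection list that follows records conversion among patients who began as RIS or CIS, so some are expected in the MS group.

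The documents give no power calculation, precision target or success threshold for test 1. They do not say how 50 MS patients would be chosen from the larger pool, or with what RRMS/progressive mix.

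**The concern.** Test 2 alone puts at least 100 MS samples on the assay, whatever the overlap between cohorts. Applying an already published model to the remaining MS profiles is computation only. The stated test 1 set nevertheless uses 50 of them, so the MS side of the validation is estimated from half the available data.

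What is at stake is precision. Sensitivity depends only on the number of MS patients and is affected most. AUROC depends on both groups and is affected less. Specificity is not affected. Drawing 50 of 100 adds no separate harm beyond this loss, and nothing in the documents points to bias. The differing CIS/RIS wording matters here because it decides who is eligible for the larger set.

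**Working it through.** **The plan's own figures.** There is no power or precision calculation to reproduce. The counts agree: 25 + 25 = 50 controls; 50 + 50 = 100 for test 1; 50 + 25 + 25 = 100 MS for test 2; the site targets sum to 100 MS and 50 non-MS.

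**Inputs.** From the documents: A = 0.98 (Synopsis), nC = 50 controls, nMS = 50 as stated, 100 available, and 130 at the top of the Figure 1 range. Assumed, because the documents do not give them: score distributions, observed sensitivity, the 95% level, and 80–90 eligible patients under a strict CIS/RIS reading.

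**AUROC standard error.** The Mann–Whitney variance is

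SE² = [A(1−A) + (nMS−1)(P1−A²) + (nC−1)(P2−A²)] / (nMS·nC),

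where P1 is the probability that two random MS scores both exceed one control score, and P2 the probability that one MS score exceeds two random control scores. A(1−A) = 0.0196 and A² = 0.9604.

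*Equal-variance binormal.* Numerical integration gives P1 = P2 = 0.96339, so each difference from A² is 0.002987.
- 50 MS: (0.0196 + 98 × 0.002987)/2500 = 0.0001249; SE 0.0112.
- 100 MS: (0.0196 + 148 × 0.002987)/5000 = 0.0000923; SE 0.0096, 14% smaller.

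*Hanley–McNeil, MS as cases.* P1 = A/(2−A) = 0.96078 and P2 = 2A²/(1+A) = 0.97010; the differences are 0.000384 and 0.009701.
- 50 MS: (0.0196 + 49 × 0.000384 + 49 × 0.009701)/2500 = 0.0002055; SE 0.0143.
- 100 MS: (0.0196 + 99 × 0.000384 + 49 × 0.009701)/5000 = 0.0001066; SE 0.0103, 28% smaller.
- With the roles of the groups swapped: 0.0143 to 0.0141, 1% smaller.

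SE by number of MS patients, 50 controls, A = 0.98:

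| Score model | 50 | 80 | 90 | 100 | 130 | Reduction, 50 to 100 |
|---|---|---|---|---|---|---|
| Equal variance | 0.0112 | 0.0100 | 0.0098 | 0.0096 | 0.0092 | 14% |
| MS SD 1.5 × control SD | 0.0121 | 0.0101 | 0.0096 | 0.0093 | 0.0085 | 23% |
| Control SD 1.5 × MS SD | 0.0121 | 0.0116 | 0.0115 | 0.0114 | 0.0113 | 5.5% |
| Hanley–McNeil, MS as cases | 0.0143 | 0.0115 | 0.0108 | 0.0103 | 0.0092 | 28% |
| Hanley–McNeil, swapped | 0.0143 | 0.0142 | 0.0142 | 0.0141 | 0.0141 | 1% |

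A simulation of the three binormal rows (40,000 replicates) gave 0.0113/0.0096, 0.0121/0.0092 and 0.0120/0.0115 at 50/100 MS. If the validation AUROC were only 0.90, the equal-variance reduction is still 14% (0.0302 to 0.0261).

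**Sensitivity, Clopper–Pearson 95% CI.**

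| Assumed sensitivity | MS patients | CI | Width | Narrower than at 50 |
|---|---|---|---|---|
| 90% | 45/50 | 0.782–0.967 | 0.185 | – |
| 90% | 72/80 | 0.812–0.956 | 0.143 | 22% |
| 90% | 81/90 | 0.819–0.953 | 0.135 | 27% |
| 90% | 90/100 | 0.824–0.951 | 0.127 | 31% |
| 90% | 117/130 | 0.835–0.946 | 0.111 | 40% |
| 80% | 40/50 to 80/100 | 0.663–0.900 to 0.708–0.873 | 0.237 to 0.165 | 30% |
| 96% | 48/50 to 96/100 | 0.863–0.995 to 0.901–0.989 | 0.132 to 0.088 | 33% |

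**Specificity.** n stays at 50; at 45/50 the CI is 0.782–0.967 before and after.

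**Balanced accuracy** at 90% sensitivity and specificity: SE = ½√(0.09/50 + 0.09/50) = 0.030, against ½√(0.09/100 + 0.09/50) = 0.026, 13% smaller.

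**Choosing 50 of 100.** The variance from the draw is 0.09/50 − 0.09/100 = 0.0009. This is the same variance that the larger set removes, so it must not be counted twice.

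**The case against.** The strongest reply is that no error is shown. The counts are consistent, a balanced 50:50 set is a legitimate design, and item 3 read plainly may already give every assayed patient an MS probability. For AUROC, the only performance measure the protocol names for this test, the 95% half-width moves only from 1.96 × 0.0112 = 0.022 to 1.96 × 0.0096 = 0.019. With no precision target or threshold, no decision is shown to change. All of this supports calling the point minor. It does not remove it, because calculating a probability does not put a patient in the analysis set, and that set is stated as 50 + 50 in both item 1 and Figure 1.

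A second reply concerns case mix. Using everyone ties pooled results to the roughly 50:50 RRMS:progressive quota. If sensitivity differed by 10 points between the two and the target mix were 80:20 (both assumed), the shift would be 0.10 × (0.80 − 0.50) = 0.03. At 90% sensitivity and n = 100, the root-mean-square error is then √(0.030² + 0.03²) = 0.042, no better than 50 patients drawn to the target mix, √(0.09/50) = 0.042. The arithmetic is right, but the plan gives its 50 no target mix, so the advantage of the smaller set is hypothetical. The case-mix cost itself is real and has to be disclosed.

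Third, a 2:1 set breaks the equality of percent-correct and balanced accuracy that holds at 50:50. That is true, but AUROC, sensitivity and specificity do not depend on the ratio.

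Finally, the CIS/RIS statements can be read as compatible, since a converted patient has definite MS, and the placement of the Figure 1 note may be affected by text extraction. That reading also supports at least 100 eligible patients. Two different wordings still leave the analysis set open to interpretation.

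**Conclusion.** The concern holds as a cheap gain in precision that the plan leaves unused. It does not invalidate the validation. From 50 to 100 MS patients with 50 controls, the AUROC standard error falls by about 14% under equal-variance scores, with a range of 1–28% that depends on which group's scores vary more, something the documents do not tell us. The sensitivity CI narrows by 30–33% at assumed sensitivities of 80–96%. If a strict CIS/RIS reading left only 80–90 patients (assumed; no count is given), the gain would be 22–27% for sensitivity at 90% and 10–12% for the equal-variance AUROC SE. With 130 patients it would be 40% and 18%. Specificity is unchanged throughout. The premise that at least 100 MS samples are assayed follows directly from item 2 and does not depend on the overlap; that at least 100 are eligible follows from the Figure 1 CIS/RIS wording with the Section 2.1 diagnosis criterion.

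**What to change.** In the Synopsis (Aim 1), Section 1 item 1 and Figure 1, define the test 1 MS set as all eligible assayed MS patients (at least 100 under the Figure 1 CIS/RIS wording), fixed before unblinding, against the 50 controls. Then:

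- Report AUROC, sensitivity (overall and by RRMS, PPMS and SPMS) and specificity (overall and by NIND and OIND), each with a CI.
- If the accuracy analysis in item 3 means a pooled percent-correct, do not use it, because it would depend on the 2:1 ratio.
- Use one CIS/RIS wording in item 1 and Figure 1.
- State that pooled sensitivity and AUROC reflect the roughly 50:50 RRMS:progressive quota, and that subtype results are descriptive. With 25 patients the interval is wide: 22/25 gives 0.688–0.975.

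The cost is wording in three places, with no added patients, visits or assays. Section 5 requires protocol modifications to be reviewed by the IRB or ethics committee at each site, so an amendment is needed. The scientific cost is the fixed case mix, which subtype reporting shows but does not remove. If the sponsor already intends to include every scored MS patient, the same edits simply state it.

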Additional data to be collected after consent is obtained:

MS Patient data collected after follow-up or phone interview visit

Access electronic medical record (EMR) to collect/confirm the following information:

- Transcribing documented neurological examination completed within 1 month of the time of LP to EDSS or NeurEx.
- Detailed DMT history (with estimated date of initiation and termination of all drugs).
- Documentation of proximity of clinical relapse or contrast enhancing lesions (CELs) to the initial I P
- Estimation of subsequent relapse rate; conversion to clinically-definite MS (for original RIS/CIS) and possibly SPMS (for original RRMS).
- Imaging Data
 - If available, Brain MRI \pm 3 month of the **LP date:**
 - If images available transfer de-identified MRI images
 - If images are not available collect the following information:
 - 1) CEL if MRI done within a month from LP
 - 2) T2 lesion load (for MRI done within 3 months from LP)
 - 3) T1 black holes
 - If available, spinal cord MRI \pm 3 months of LP date:
 - If images available transfer de-identified MRI images
 - If images are not available collect the following information:
 - 1) CEL if MRI done within a month from LP
 - 2) T2 lesion load (for MRI done within 3 months from LP)
 - If available, Brain MRI (within 1 year of follow-up visit):

- If images available transfer de-identified MRI images
- If images are not available collect the following information:
 - 1) CEL if MRI done within a month from the follow-up visit
 - 2) T2 lesion load
 - 3) T1 black holes
- Spinal cord MRI around the time of follow-up visit:
 - If images available transfer de-identified MRI images
 - If images are not available collect the following information:
 - 1) CEL if MRI done within a month from follow-up visit
 - 2) T2 lesion load
- Available information for calculating BREMSO score (i.e., symptom onset: sphincter, motor, sensory; number of neurological functional systems involved at onset; incomplete recovery at onset).
- If available, 25FW/9HPT around the time of initial LP.

MS Patient data collected under consent waiver

Access electronic medical record (EMR) to collect/confirm the following information:

- Transcribing documented neurological examination completed within 1 month of the time of LP to EDSS or NeurEx.
- Transcribing documented most recently completed neurological examination available in medical record to EDSS or NeurEx.

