- Detailed DMT history (with estimated date of initiation and termination of all drugs).
- Documentation of proximity of clinical relapse or contrast enhancing lesions (CELs) to the initial LP
- Estimation of subsequent relapse rate; conversion to clinically-definite MS (for original RIS/CIS) and possibly SPMS (for original RRMS).
- Available information for calculating BREMSO score (i.e., symptom onset: sphincter, motor, sensory; number of neurological functional systems involved at onset; incomplete recovery at onset).
- If available, 25FW/9HPT around the time of initial LP.

Non-MS Patient data collected after follow-up visit:

- Access electronic medical record (EMR) to confirm the clinical diagnosis.
- Contact the patient on the phone to confirm their availability to be contacted by the NIH to sign their consent.

2.3 Targeted patient number for each SPINCOMS center.

Table 1.

	MS patients	Non-MS patients	
	All require in-person follow-up visit	Do not require in-person follow-up but require data collection	
Wash. U	60 (30 RRMS, 30PMS)	30 (~15 NIND, ~15 OIND)	
U. Ottawa	20 (10 RRMS, 10PMS)	10 (~5 NIND, ~5 OIND)	
U. Colorado	20 (10 RRMS, 10PMS)	10 (~5 NIND, ~5 OIND)	
NIAID/NDS	None budgeted, but will contribute all available that are non-overlapping and unpublished	None budgeted, but will contribute all available that are non-overlapping and unpublished	

^{*}University of Montana will not participate in patient recruitment, data analysis only

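### Does the undated RRMS/SPMS/PPMS label leave patients who convert to SPMS after the lumbar puncture without a group?

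*Combined protocol and SAP*

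**What the plan says.** Section 1, item 2, sets the groups for the second cohort: "we will select CSF from 50 RRMS and 50 progressive MS patients (25 SPMS and 25 PPMS". Item 4 sets the same split for the severity cohort. Figure 1 adds an overall requirement, "Required: ≥ 50 RRMS, ≥ 25 PPMS, ≥ 25 SPMS", to be met from a pool described as "Select n=100-130 eligible MS patients", and notes that "The cohorts of MS patients in 1-3 can overlap". Table 1 in Section 2.3 divides the numbers by site; the entry for the largest site is "60 (30 RRMS, 30PMS".

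None of these places dates the subtype. Section 2.1 dates only the diagnosis of MS itself, by 2017 McDonald criteria at the follow-up visit, which must fall at least 3 years after the LP.

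The protocol does expect some patients to change subtype. Both chart-abstraction lists for MS patients in Section 2 include "conversion to clinically-definite MS (for original RIS/CIS) and possibly SPMS (for original RRMS". That item requests no date, whereas the treatment item in the same lists does: "Detailed DMT history (with estimated date of initiation and termination of all drugs". For patients studied under the consent waiver, the list also includes "Transcribing documented most recently completed neurological examination available in medical record to EDSS or NeurEx".

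**The concern.** The subtype does two jobs. It fills the quotas at each site, and in the second cohort it is the reference standard against which the CSF score is judged. LP and follow-up are at least 3 years apart, so some patients who were RRMS when the CSF was taken may be SPMS when seen again. Without a stated date, one site could enter such a patient as RRMS and another as SPMS.

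The quotas could suffer too. If k of the 25 SPMS places go to patients who converted after the LP, a label taken at LP leaves 25 − k SPMS. If k patients in RRMS places convert, a follow-up label leaves 50 − k RRMS. Either falls short of the Figure 1 minimum when the pool is exactly 100.

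The abstraction item carries no conversion date, so on a literal reading the listed fields might not separate conversion before the LP from conversion after it. If the label date were still open when the scores are unblinded, the AUROC would depend on a choice made with the results in view. Most of the severity cohort would share the same labels.

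**Working it through.** **Counts.** The plan's own numbers reproduce from Table 1. MS patients: 60 + 20 + 20 = 100. RRMS: 30 + 10 + 10 = 50. Progressive: 30 + 10 + 10 = 50, matching 25 + 25. With two cohorts of 100 drawn from at most 130 patients, at least 100 + 100 − 130 = 70 belong to both. The documents give no power or precision target to reproduce.

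**Which date does the text suggest?**
- Towards LP: Section 1 calls the studies cross-sectional. What is selected is the CSF of RRMS or progressive patients. The abstraction item speaks of conversion in patients whose *original* form was RRMS, follows an item about the initial LP, and opens with relapses subsequent to it.
- Towards follow-up: the MS diagnosis is dated at that visit. For the first cohort, Figure 1 accepts CIS/RIS patients who later progressed to definite MS.

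The balance favours LP, by inference only. On that reading a post-LP converter stays RRMS, and the conversion item already records a post-LP event.

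**When is the label fixed?** In Section 1 patients are selected by group, their CSF is assayed blind, the published models are applied, and only then are results unblinded. A quota label therefore exists before any score is seen.

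**How much could it matter?** From the documents: AUROC 0.91 (Synopsis) and 50 versus 50. Assumed, because the documents are silent: k post-LP converters among the SPMS places; a, the AUROC of converters against RRMS; and binormal scores with equal variance.

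- Progressive versus converter: P = Φ(Φ⁻¹(0.91) − Φ⁻¹(a)) = Φ(1.341 − Φ⁻¹(a)), which is 0.910, 0.793 and 0.691 for a = 0.5, 0.7 and 0.8.
- Follow-up label: [0.91(50 − k) + a·k]/50. For k = 10, a = 0.7: (36.4 + 7.0)/50 = 0.868.
- LP label, converters moved to RRMS without replacement: [50 × 0.91 + k·P]/(50 + k). For k = 10, a = 0.7: (45.5 + 7.93)/60 = 0.890.

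| k | a | LP label | Follow-up label | Difference |
|---|---|---|---|---|
| 5 | 0.5 | 0.910 | 0.869 | +0.041 |
| 5 | 0.7 | 0.899 | 0.889 | +0.010 |
| 5 | 0.8 | 0.890 | 0.899 | −0.009 |
| 10 | 0.5 | 0.910 | 0.828 | +0.082 |
| 10 | 0.7 | 0.890 | 0.868 | +0.022 |
| 10 | 0.8 | 0.874 | 0.888 | −0.014 |

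The two labels give equal AUROC at a = 0.756 for k = 5 and 0.763 for k = 10. If quotas are instead filled on LP status and 10 of the 50 RRMS later convert, the LP label gives 0.910/0.887/0.866 and the follow-up label 0.842/0.875/0.892 for the same three values of a, with the crossing at 0.734. The sign of the effect is therefore unknown.

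**Against sampling error.** The Hanley-McNeil standard error at 0.91 with 50 versus 50 is 0.0305, so the 95% half-width is 1.96 × 0.0305 = 0.060. Both labels are applied to the same patients, so the paired difference is the closer comparison. In 10,000 simulated studies at k = 10, LP minus follow-up had a 95% range of 0.030 to 0.131 (a = 0.5), −0.033 to 0.077 (a = 0.7) and −0.067 to 0.040 (a = 0.8). Leaving the 10 converters out returns 0.910 under this model, with half-width 0.066 (40 versus 50).

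**The case for a change.** The best case for a change is that a lean is not a rule. The work is presented as a step towards regulatory approval, and a validation AUROC should rest on a reference label fixed in writing. Two careful sites could read the protocol differently, and one sentence plus one date field would settle it. If converters' CSF at LP looks just like RRMS, ten of them move the expected AUROC by 0.082, which is more than sampling error.

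Part of this stands. The date is not written down, sites could differ on a handful of patients, and the a = 0.5 case cannot be excluded from the documents.

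The rest is weaker:
- An open choice after unblinding fits poorly with a label already used to fill the groups. Relabelling is not expressly forbidden, but it would visibly break the 50/50 design.
- The waiver item yields a disability scale, not a subtype, so it is not a competing source of the label.
- Table 2 makes chart review of disease history mandatory for in-person, phone and waiver patients, and Section 3.1 adds the patient questionnaire. The questionnaire is not in the documents. A conversion date is not required by the listed items, but it may be recoverable from these sources.
- A quota shortfall is bounded by the extra 0 to 30 patients in the pool and by unbudgeted NIAID/NDS cases. If sites use LP status from the outset, the SPMS shortfall does not arise.
- The natural choice of date is the one used to develop the published classifier. That source is not available here and may already settle the matter.

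**Conclusion.** No change to the plan is needed. The protocol leaves out a detail; it does not state a rule that gives a wrong result. The text leans towards status at LP, the groups are formed before scores are seen, and analysts with chart access can identify post-LP converters and report the classifier with and without them.

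Neither the size nor the direction of any effect can be determined from the documents. With 5 to 10 converters and intermediate scores (a of 0.7 to 0.8), the expected AUROC differs by about 0.01 to 0.02, in either direction, against a half-width of 0.060. A clear effect at k = 10 requires converters who look exactly like RRMS at LP. These figures rest on an assumed k and a, the binormal model, and a true AUROC equal to the development value of 0.91. The effect on the severity cohort was not quantified.

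### The RRMS-versus-progressive classifier is judged only on its own accuracy, with no planned comparison with age or disability at lumbar puncture, so as written the study will not show value beyond routine clinical data.

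*Combined protocol and SAP*

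**What the plan says.** The Synopsis reports a development AUROC of 0.91 for this test from a single centre, with no confidence interval and no clinical comparator. It gives the reason for the study as "it is imperative to determine their performance in real clinical practice settings", and Aim 1 is "To independently validate afore-mentioned CSF-biomarker-based tests for their clinical value". Clinical value is not defined.

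Section 1 (Study Design) gives the sample: "we will select CSF from 50 RRMS and 50 progressive MS patients (25 SPMS and 25 PPMS". The analysis is stated in two sentences: "Probability of MS diagnosis and progressive MS diagnosis will be calculated based on published models", and "Results will then be unblinded and analyzed for accuracy of diagnostic conclusion". The contents page lists a Data Analyses section, but the body contains none. No comparator, matching or adjustment is described anywhere.

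Section 2 does provide for some clinical data from around the LP. One item is "Transcribing documented neurological examination completed within 1 month of the time of LP to EDSS or NeurEx"; another is "Available information for calculating BREMSO score". In Table 2 the NeurEx entry for the time of LP is marked as collected only if available. Age is not named as a data item.

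**The concern.** This test predicts a label, RRMS or progressive MS, that clinicians already assign from history and examination. If progressive patients tend to be older or more disabled at LP, any CSF score that follows age or disability will separate the two groups to some extent. An AUROC judged against chance cannot tell such a score from one that carries disease-specific information.

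What is at stake is how a good result would be read. The Synopsis presents the study as a step towards regulatory approval. A replicated AUROC near 0.91 could be reported as validated clinical value while nobody knows how much of it a date of birth would have delivered in the same patients.

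**Working it through.** **Inputs from the documents.** Development AUROC 0.91 (Synopsis); 50 RRMS and 50 progressive patients (section 1). The documents state no alpha, power, margin or success criterion for this test, so there is no calculation of theirs to reproduce. They give no age or EDSS distributions either.

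**Step 1: what accuracy alone can show.** The Hanley-McNeil variance is

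[A(1−A) + (n1−1)(Q1−A²) + (n2−1)(Q2−A²)] / (n1·n2), with Q1 = A/(2−A) and Q2 = 2A²/(1+A).

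For A = 0.91 and n1 = n2 = 50: Q1 = 0.8349, Q2 = 0.8671, A² = 0.8281. The variance is (0.0819 + 0.331 + 1.912)/2500 = 0.00093, so SE = 0.0305. The 95% CI is 0.91 ± 1.96 × 0.0305, or 0.85 to 0.97. Power against 0.5 is close to 100%. Discrimination better than chance is almost sure to be confirmed if the development figure holds.

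**Step 2: what age alone might give (assumed range).** For one normally distributed predictor with equal SDs, AUROC = Φ((mean difference/SD)/√2).

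- Gap 10 years, SD 10: Φ(0.707) = 0.760
- Gap 15 years, SD 10: Φ(1.061) = 0.856

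On the scale from chance (0.5) to 0.91, age alone would then cover (0.760−0.5)/0.41 = 63% to (0.856−0.5)/0.41 = 87% of the distance.

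**Step 3: what the planned sample can say about a comparator.** A binormal simulation (1,500 runs per cell) of the paired DeLong test, two-sided 5%, set a classifier with AUROC 0.91 against a comparator measured in the same 50 + 50 patients. The comparator AUROCs and within-group correlations are assumptions. Entries are the power to show that the classifier is better.

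| Comparator AUROC | Correlation 0 | 0.3 | 0.6 |
|---|---|---|---|
| 0.70 | 95% | 99% | about 100% |
| 0.75 | 81% | 91% | 99% |
| 0.80 | 55% | 67% | 86% |
| 0.85 | 22% | 27% | 41% |
| 0.90 | 4% | 5% | 5% |

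These figures apply to the head-to-head contrast, not to the gain from adding the score to a model.

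**Step 4: equal AUROCs do not mean no added information.** Under the same binormal model, a comparator of 0.90 combined optimally with a score of 0.91 reaches 0.968, 0.948 and 0.929 at correlations 0, 0.3 and 0.6. The gains over the comparator are 0.068, 0.048 and 0.029. The comparison and the added information therefore have to be estimated separately.

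**Step 5: the method for the gain.** When the score is added to a model refitted in the same 100 patients, the two models are nested and DeLong is not calibrated. In a simulation with a score that added nothing (comparator 0.92), it rejected in 0 to 0.2% of runs instead of 5%.

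**The case against.** The strongest reply is that the plan does what it sets out to do. The sentence before Aim 1 explains that the results come from one centre and that performance in practice settings is needed. Blinded scoring of new patients with a locked model answers that. Value over bedside data is a further question, and the protocol does not explicitly promise to answer it. This stands in part: clinical value is undefined, and an accuracy analysis does serve one reasonable meaning of it. It does not serve the other meaning, and nothing tells the reader which is intended.

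A second reply is that the published model may already handle age. The documents do not say. Even if it does, that would not show what age achieves alone in these patients.

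A third is that EDSS is a doubtful yardstick. The phenotype label is a clinical judgement about the course of disability, so EDSS at LP may share information with the reference label and its AUROC may be inflated. This stands, and it is why age should be the primary comparator.

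Three stronger readings should be resisted:

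- A reader might infer that the study cannot show clinical value. The gap is in the stated analysis. Nothing in the design prevents the comparison, and 50 against 50 has useful power against a moderate comparator.
- A reader might infer that the CSF test adds nothing, since an assumed EDSS gap of 2 to 3 points with SD 1.5 gives Φ(0.943) = 0.827 to Φ(1.414) = 0.921, which reaches 0.91. Those gaps are not in the documents, and step 4 shows that matching AUROCs are compatible with real added information.
- A reader might take the BREMSO items as support for the same point. They bear on prognosis, are collected only as available, and do not support a claim about the RRMS-versus-progressive classifier.

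**Conclusion.** The point holds as a gap in the analysis plan. Section 1 judges this classifier on its own accuracy, and no section plans a benchmark from age or disability at LP. As written, the study can confirm discrimination in new patients but will not show value beyond routine clinical data.

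The size is conditional. The age-only AUROC of about 0.76 to 0.86 rests on an assumed gap of 10 to 15 years, an SD of 10 and normal distributions, and the true gap in these cohorts could be smaller or larger. The range does not show that the CSF score fails, since its upper end is still below 0.91. It shows that 0.91 cannot be interpreted without the benchmark. The improvement is cheap and worth making before unblinding.

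**What to change.** 1. Keep the published score locked and unchanged.
2. Name age at LP as a data item and record it for every patient in this cohort.
3. In the same patients, report the AUROC of age at LP alone beside that of the CSF score, with the paired difference and its 95% CI (DeLong or bootstrap).
4. Report the added information of the score over age by a likelihood-ratio test in a logistic model, with an optimism-corrected bootstrap estimate of the AUROC gain. Do not use DeLong on the nested models.
5. As a secondary comparison, report age plus EDSS at LP in patients with an examination near LP. State how many lack one, and state that EDSS may partly inform the phenotype label.
6. Say in Aim 1 what clinical value means, and limit the conclusion for this test to discrimination unless added value over age is shown.

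The cost is one extra data item and a little more analysis; no new patients or assays are needed. The result may be less favourable than accuracy alone. Patients without an examination near LP drop out of the secondary comparison. Precision is limited if the comparator is strong: at a comparator AUROC of 0.85 the head-to-head power is about 22 to 41% under the assumed correlations, and it is lower above that. The paired estimate and its interval should therefore carry the conclusion, rather than a significance test.
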